6.2.1.1.2 Schedule B

Schedule B will be initiated after preliminary safety data of AMG 673 in Schedule A (eg, MTD1 is estimated to be \geq 72 μ g) become available and may be conducted in parallel with Schedule A per sponsor's decision. For Schedule B, planned dose levels (dose per infusion) for the dose escalation cohorts are as follows: 72 μ g, 110 μ g, 160 μ g, 240 μ g, 360 μ g, 480 μ g and higher if MTD is not reached. The drug will be administered as short term IV infusions (approximately 30 minutes to 3 hours). The starting dose for the first

cohort on Schedule B will be 72 µg administered as short-term IV infusions daily (QD) during the 14-day cycle 1. No significant AMG 673 accumulation following QD dosing is predicted based on the preliminary PK analysis of Schedule A dosing. The doses administered for the cohorts following cohort 1 will include step-up doses administered in 2 day increments after the previous step-up dose (eg, cohort 2 will start with 72 µg for 2 days followed by 110 µg administered from day 3 to day 14; cohort 3 will start with 72 µg for 2 days followed by 110 µg from day 3 to day 4, followed by 160 µg from day 5 to day 14, etc). See [Table 3](#) below for more details.

Table 3. Schedule B - Cycle 1 Dosing

	D1 ^c	D2 ^c	D3	D4	D5	D6	D7	D8	D9	D10	D11	D12	D13	D14
Cohort 1	72 ^{ab}	72	72	72	72	72	72	72	72	72	72	72	72	72 ^b
Cohort 2	72 ^{ab}	72	110 ^{ab}	110	110	110	110	110	110	110	110	110	110	110 ^b
Cohort 3	72 ^{ab}	72	110 ^a	110	160 ^{ab}	160	160	160	160	160	160	160	160	160 ^b
Cohort 4	72 ^{ab}	72	110 ^a	110	160 ^a	160	240 ^{ab}	240	240	240	240	240	240	240 ^b
Cohort 5	72 ^{ab}	72	110 ^a	110	160 ^a	160	240 ^a	240	360 ^{ab}	360	360	360	360	360 ^b
Cohort 6	72 ^{ab}	72	110 ^a	110	160 ^a	160	240 ^a	240	360 ^a	360	480 ^{ab}	480	480	480 ^b

D = dose; Unit of dosage = µg

^a Dexamethasone 8 mg IV will be administered 1 hour prior to dose.

^b Additional PK samples will be taken at these time points as described in [Table 12-Table 14](#).

- [Table 13](#) PK sampling will be used only at the first dose of the target dose (highest dose planned) to be tested in Cycle 1 for each subject
- All subjects will undergo day 1 PK sampling as described in [Table 12](#).

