- PK sampling will occur on day 14-19 of Cycle 1 per [Table 12](#) if the subject will not receive cycle 2 immediately following cycle 1. If subject proceeds to Cycle 2, day 14 (post-dose) through day 19 samples will not be collected and Cycle 2 day 1 (eg day 15 after 1st dose) should be collected per [Table 14](#).

^c Upon recommendation of DLRT and Sponsor agreement, a lower starting dose may be used (eg, 36 µg) for up to the first 2 doses

The DLRT may recommend shortening the duration of steps to 1 day or to extend the duration of steps up to 5 days based on the emergent safety, PK and PD data. If the duration of step-up doses is extended, the duration of a cycle can be extended from 14 days to 28 days. All subjects will be pre-treated with an 8-mg dose of IV dexamethasone 1 hour prior to AMG 673 dose on day 1 and prior to each step-up dose of AMG 673.

Cycle 2 will consist of 4 AMG 673 infusions: day 1, day 4, day 8, and day 11 of a 14-day cycle at the target dose (maximum planned dose received from cycle 1) (see [Table 4](#) below). Cycle 1 schedule may be repeated 1 time before cycle 2 schedule is initiated upon agreement between the Investigator and Sponsor if the patient will likely

Approved

gain additional benefit per Investigator's assessment. If cycle 1 is not repeated, cycle 2 should begin immediately after cycle 1 with no dose free interval.

Table 4. Schedule B – Cycle 2 and Higher Dosing

	Day of Dose (14-Day Cycle)													
	1	2	3	4	5	6	7	8	9	10	11	12	13	14
Cohort 1	72 ^a			72				72			72			
Cohort 2	110 ^a			110				110			110			
Cohort 3	160 ^a			160				160			160			
Cohort 4	240 ^a			240				240			240			
Cohort 5	360 ^a			360				360			360			
Cohort 6	480 ^a			480				480			480			

Unit of dosage = µg

^a Dexamethasone 8 mg IV will be administered 1 hour prior to dose.

Upon recommendation from DLRT, the number of AMG 673 infusions in cycle 2 and higher may be adjusted based on emergent PK, safety, and PD data (eg, weekly [day 1 and day 8 of each cycle]). Subjects will be hospitalized for the whole duration of cycle 1 (ie, a minimum of 15 days), and for at least 48 hours after each AMG 673 administration in cycle 2 and higher. In the absence of any DLTs or SAEs, shorter hospitalization may be considered upon PI recommendation and Medical Monitor agreement after Cycle 2.

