DISEASE and BIOMARKER ASSESSMENTS																																											
Bone marrow assessments	X																																								X ^k		X

Footnotes defined on next page of the table

Approved

EOS = End of Study; EOT = End of Treatment; SCR = Screening

- ^a Assessments should be taken at the time specified (in hours) from the start of infusion on that day. If a time is not specified, all assessments and collections should be pre-dose.
- ^b The following assessments should be performed relative to the day 14 dose. Cycle 2 should begin immediately after Cycle 1 with no treatment free interval (see [Section 6.2.1.1.2](#)). The samples in dark gray are only collected if the subject will not initiate cycle 2 immediately after cycle 1. If cycle 2 is initiated immediately after cycle 1, then collect per [Table 14](#) (refer to footnote J).
- ^c Clinical evaluations will include physical exam, ECOG, and weight. Screening only: demographics, medical history, and height will also be obtained. Pre-dose clinical evaluation may occur up to 3 days prior to dose.
- ^d Vital signs / pulse oximetry must be collected as described above but may be collected at site more frequently per institutional policy or by recommendation of PI. Additional assessments do not need to be reported to EDC unless related to an adverse event but must be kept in source. Subjects will also be assessed prior to discharge from hospital in order to detect possible signs and symptoms of infusion reactions.
- ^e ECGs are required per [section 7.3.8](#). ECG's: At screening 2 triplicates (total of 6 ECGs) should be done, at predose C1D1: 1 triplicate (total of 3 ECGs), post 1hr -end of infusion, 24 hours post dose and at EOS. Schedule for ECGs during cycle 1 also applies in case of intra-subject dose escalation, regardless of actual study cycle.
- ^f Serum pregnancy test will be performed for all females unless surgically sterile or > 2 years postmenopausal
- ^g Refer to [Table 3](#) for planned dosing regimen

ⁱ This sample is optional. See Laboratory Manual for details on collection requirements.

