^j Cycle 1, PK samples must always be collected on day 1. In addition, enhanced PK sampling, as described in [Table 13](#), is required at the time of step-up to the maximum planned dose. This is outlined [Table 3](#). If subject is not planned to immediately initiate cycle 2 (eg, due to DLTs), day 14-19 PK samples should be collected. If subject proceeds to Cycle 2, day 14 (post dose)-19 PK samples are not collected and sampling should occur as described in [Table 14](#).

^k During the same procedure, bone marrow samples will be collected for both response and biomarker assessments. This sample is to be collected after the last dose in Cycle 1 (ie, day 14).

Approved

Table 13. Schedule of Assessments: Schedule B (Cycle 1 Step-Up Dose Visit)

Step-Up Dose Day ^a	Treatment Period ^a											
	1											2
	Pre-dose	0	1	2	3	4	6	8	12	16	20	Pre
GENERAL AND SAFETY ASSESSMENTS												
Dexamethasone administration 1 hr before prior	X											
Clinical Evaluation ^c	X											X
Vital signs, pulse oximetry ^d	X	X	X	X	X	X	X	X	X	X	X	X
ECG triplicate measurement ^e	X	X ^f										X
LABORATORY ASSESSMENTS												
Coagulation	X						X					X
Hematology, Chemistry	X						X					X
Urinalysis	X											
INVESTIGATIONAL PRODUCT DOSING												
AMG 673 short term IV Infusion		X										X
PK ASSESSMENTS												
AMG 673 PK Collection ^f	X	X				X	X					X

EOS = End of Study; EOT = End of Treatment; SCR = Screening

^a Step-up doses are defined in Table 3. Day 1 in this schedule is each day where the planned dose is higher than the previous day.

^b Hours are calculated from the start of initial infusion of the higher dose (step-up)

^c Clinical evaluations will include physical exam, ECOG, and weight. Screening only: demographics, medical history, and height will also be obtained. Pre-dose clinical evaluation may occur up to 3 days prior to dose.

^d Vital signs / pulse oximetry must be collected as described above but may be collected at site more frequently per institutional policy or by recommendation of PI. Additional assessments do not need to be reported to EDC unless related to an adverse event, but must be kept in source.

^e ECGs are required per section 7.3.8. Triplicate ECGs are required at the times described above.

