^d Vital signs / pulse oximetry will also be assessed prior to subject's discharge from hospital in order to detect possible signs and symptoms of infusion reactions.

^e ECGs are required per [section 7.3.8](#). ECG should be taken at the end of the infusion of the first dose in each cycle.

^f Serum pregnancy test will be performed for all females unless surgically sterile or > 2 years postmenopausal

^h This sample is optional. See Laboratory Manual for details on collection requirements.

ⁱ PK samples are required as shown for cycles 2, 3, 5 and 8 only in addition to EOT/EOS visits.

^j PK samples only collected during cycle 2 and not subsequent cycles. If Cycle 2 is not initiated immediately after Cycle 1, collect samples on day 14-19 relative to initiation of Cycle 1 per [Table 12](#).

^k During the same procedure, bone marrow samples will be collected for both response and biomarker assessments.

Approved

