### 9.6.6 Electrocardiogram

All on-study electrocardiogram (ECG) data will be listed and select parameters of interest may be plotted.

Summaries over time and/or changes from baseline over time will be provided for all ECG parameters.

The analysis of Fridericia's (QTcF) QT correction will use the results recorded on the CRF. Subjects' maximum change from baseline in QT interval corrected by Fridericia's formula will be categorized into the following groups per their maximum change from baseline in QTcF. Unscheduled assessments will be included in the determination of the maximum change.

[figure not shown]
- $\leq 30$  msec
- $>30 - 60$  msec
- $>60$  msec

The number and percentage of subjects in each group will be summarized.

Subjects will also be categorized into the following groups per their maximum post baseline QTcF. Unscheduled assessments will be included in the determination of the maximum post baseline value.

- $\leq 450$  msec
- $>450 - 480$  msec
- $>480 - 500$  msec
- $>500$  msec

The number of subjects in each group will be summarized for each dosing group.

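### In Schedule B the number of scheduled ECGs rises with the dose cohort, so the by-dosing-group table of each subject's maximum QTcF is not like for like in its lower outlier categories

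*SAP*

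**What the plan says.** **Collection.** Protocol 7.1, Table 12 (Schedule B, cycle 1), sets the ECGs around the first dose as "at predose C1D1: 1 triplicate (total of 3 ECGs), post 1hr -end of infusion, 24 hours post dose and at EOS". Table 13 adds ECGs at step-ups: its ECG row marks pre-dose, end of infusion and next-day pre-dose. Its footnotes say "Triplicate ECGs are required at the times described above" and "Day 1 in this schedule is each day where the planned dose is higher than the previous day". The restriction to the step that reaches the target dose is written for PK sampling, not for ECGs.

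**Steps.** Protocol 6.2.1.1.2 says "The doses administered for the cohorts following cohort 1 will include step-up doses administered in 2 day increments after the previous step-up dose". Table 3 shows 0, 1, 2, 3, 4 and 5 step-ups in cohorts 1 to 6.

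**Analysis.** SAP section 5 sets the ECG baseline at the cycle 1 day 1 pre-dose readings, so every step-up pre-dose ECG is post-baseline. SAP 9.6.6 categorises the maximum change in QTcF (cut points 30 and 60 msec) and the maximum post-baseline QTcF (cut points 450, 480 and 500 msec). Unscheduled ECGs count in both. The sentence "The number of subjects in each group will be summarized for each dosing group" follows the second categorisation only; for maximum change the SAP does not name a split. Dosing group is not defined. Summaries over time and a listing of all ECGs are also planned.

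**The concern.** The expected maximum of a set of noisy readings grows with the number of readings. In Schedule B that number is set by the number of step-ups, and so by the target dose. Cohort 1 has no scheduled cycle 1 ECG after the 24-hour reading, although dosing continues daily to day 14; cohort 6 has readings through to day 12. A table of maxima by dosing group therefore mixes a possible drug effect with the intensity of measurement.

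Safety is the primary endpoint of this first-in-human trial, and these are the SAP's only categorical QT tables. A few readings just over 450 msec in a high cohort could be taken for a dose signal. None in cohort 1 could be taken for reassurance when it rests on few and early readings.

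**Working it through.** The documents state no ECG count, no QTcF variability and no error rate for these tables, so there is no figure of the plan's own to reproduce.

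**Step 1: count the readings.** Post-baseline time points in cycle 1 = 2 (end of infusion and 24 h after the first dose, Table 12) + 3 × number of step-ups (Table 13, Table 3). At 2-day steps no time points coincide.

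| Cohort | 1 | 2 | 3 | 4 | 5 | 6 |
|---|---|---|---|---|---|---|
| Step-ups | 0 | 1 | 2 | 3 | 4 | 5 |
| Cycle 1 time points | 2 | 5 | 8 | 11 | 14 | 17 |
| With one cycle 2 and end of study (+5) | 7 | 10 | 13 | 16 | 19 | 22 |

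The +5 is four ECG marks in Table 14 plus one at end of study. The column alignment of that table is damaged in the available text, and its footnote names only one time ("ECG should be taken at the end of the infusion of the first dose in each cycle"), so the four should be checked against the original. They are the same for every cohort and do not affect the difference of 15. With all 12 cycles the counts for cohorts 1 and 6 are 47 and 62 (2 or 17, + 11 × 4, + 1).

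**Step 2: noise-only model.** Assumptions, none of them from the documents: no drug effect; independent normal errors with SD s on each triplicate mean, s from 6 to 15 msec; subject means m distributed N(420, 15²). With k readings:

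- P(max QTcF > c) = 1 − E[Φ((c − m)/s)^k], averaged over m.
- P(max change > c) = 1 − E[Φ((c + e₀)/s)^k], averaged over the baseline error e₀ ~ N(0, s²), which all of a subject's changes share.

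**Step 3: results, cohort 1 vs cohort 6.** Maximum QTcF above 450 msec, the categorisation that the SAP splits by dosing group:

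| s (msec) | Cycle 1 only (k = 2 vs 17) | With one cycle 2 and end of study (k = 7 vs 22) |
|---|---|---|
| 6 | 4.6% vs 10.5% | 7.9% vs 11.3% |
| 10 | 7.8% vs 22.4% | 15.5% vs 24.5% |
| 15 | 13.4% vs 42.5% | 28.9% vs 46.5% |

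Maximum change above 30 msec at s = 10, relevant if that table is also split by dose: 3.1% vs 14.4% in cycle 1, 8.2% vs 16.6% with one cycle 2 and end of study, 24.0% vs 27.0% after 12 cycles.

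The extreme categories in cycle 1: change above 60 msec is below 0.02% in both cohorts for s up to 10, and 0.45% vs 2.7% at s = 15. QTcF above 500 msec is at most about 0.1% throughout.

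**Step 4: subjects.** Protocol 5.1 allows up to 4 evaluable subjects per cohort. At s = 10 the expected number above 450 msec is 4 × 0.078 = 0.31 vs 4 × 0.224 = 0.90 in cycle 1, and 4 × 0.155 = 0.62 vs 4 × 0.245 = 0.98 with one cycle 2 and end of study.

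**Step 5: equal counts.** If every cohort contributed the same two time points (k = 2), the noise-only rates at s = 10 would be 7.8% (above 450 msec) and 3.1% (change above 30 msec) in all six cohorts.

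**The case against.** The strongest reply is that these are descriptive counts, with no test, trend or decision rule attached, in cohorts of very few subjects. Dosing group is undefined; the SAP section on exposure summarises by dosing schedule, and if that is meant here, no between-cohort table exists. That stands as far as it goes, although SAP 9.1 also provides for safety summaries by dose.

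The contrast of 2 with 17 is for cycle 1 alone, whereas the planned maximum runs over the whole study. This also stands. The contrast narrows with each further cycle, and unequal follow-up can mask or reverse it.

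The counts are not fixed. Section 6.2.1.1.2 says "The DLRT may recommend shortening the duration of steps to 1 day or to extend the duration of steps up to 5 days"; at 1-day steps the cycle 1 counts run from 2 to 12. It also allows a lower starting dose and a repeat of cycle 1, and intra-subject escalation brings cycle 1 ECGs into later cycles. These change the counts without making them equal.

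Independence is an assumption. With half the error variance decaying over 1 or 3 days (also assumed), the rates at s = 10 for change above 30 msec in cycle 1 become about 1% vs 13%, and under 1% vs about 10%. The gap remains.

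Summaries over time do not have this problem, so the categorical tables are not the only QT evidence. That is correct, but those summaries do not correct the categorical tables.

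A reader might infer that the plan compares QTcF formally between doses, or that the tables are bound to show a dose trend, including above 60 and 500 msec. The documents do not support this: there is no test, the expected counts are below one subject per cohort at s = 10, and the extreme categories hardly move in the calculation.

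**Conclusion.** The point holds in a limited form. The rise in scheduled ECGs with the Schedule B cohort follows from Tables 3, 12 and 13, and SAP 9.6.6 neither restricts the maximum to common time points nor shows the number of readings. For equal follow-up, the expected share of subjects in the lower outlier categories (above 450 msec, and change above 30 msec if split by dose) therefore rises with cohort when the drug does nothing. The direction follows from the counts; the size rests on the assumed SD, the assumed subject means and independence. It is a shift in expected rates, not a result that must appear in the data. It merits an optional change, justified mainly because the remedy uses ECGs already collected.

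**What to change.** In SAP 9.6.6:

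1. Keep both all-readings maximum tables as planned, unscheduled ECGs included, so that no outlier leaves the main safety display.
2. State that dosing group means schedule and target-dose cohort, and whether the maximum-change table is split in the same way.
3. Show the number of post-baseline ECG time points per subject beside these tables.
4. Add one Schedule B QTcF category table restricted to time points that every cohort has: end of infusion and next-day pre-dose for day 1; the same two for the first target-dose infusion; and the scheduled cycle 2 ECGs. Show the day 1 and first target-dose sets separately, because they are the same readings in cohort 1 and pooling them would make the counts unequal again. Use this table for any comparison between doses.

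The cost is SAP wording and one extra table, with no new ECGs. The first target-dose infusion falls on different study days (day 1 in cohort 1, day 11 in cohort 6 as planned), so the new table mixes dose with time on treatment; a footnote should say so. The change does not make up for the absence of scheduled ECGs late in cycle 1 in cohort 1.

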### **9.6.8 Exposure to Investigational Product**

Descriptive statistics will be produced to describe the exposure to investigational product by dosing schedule. The number of cycles, Total Number of Non-Zero Doses, number of doses of investigational product and the total dose in  $\mu\text{g}$  will be summarized.

### **9.6.9 Exposure to Non-investigational Product**

Not Applicable

### **9.6.10 Exposure to Other Protocol-required Therapy**

Not Applicable

### **9.6.11 Exposure to Concomitant Medication**

All medication will be coded using the WHO drug dictionary. A subject listing of all prior and concomitant medications will be presented.

## **9.7 Other Analyses**

All exploratory endpoints will be described in Supplemental Statistical analysis plan (SSAP) as applicable.

### **9.7.1 Analyses of Pharmacokinetic or Pharmacokinetic/Pharmacodynamic Endpoints**

Serum concentrations of AMG 673 will be determined using a validated assay. PK parameters will include, but are not limited to half-life ( $t_{1/2}$ ; if feasible), maximum observed concentration ( $C_{\text{max}}$ ), minimum observed concentration ( $C_{\text{min}}$ ), area under the concentration-time curve from time 0 to the time of the last quantifiable concentration ( $\text{AUC}_{0\text{-last}}$ ) and clearance. Pharmacokinetic parameters will be estimated using standard non-compartmental approaches and summarized by dose level using means, standard deviations, medians, minimums, and maximums.

Serum concentrations below the lower limit of quantifications will be set to zero for the estimation of the pharmacokinetic parameters for each subject and for the calculation of the summary statistic for each time point. Actual dosing and sampling time will be used for all calculations. The reasons for excluding any sample from the analyses will be provided.

Individual concentration-time data will be summarized by dose level. Individual concentration-time data will also be tabulated and presented graphically. Summary statistics will be computed for each sampling time and parameter as appropriate.

Additional PK analyses, including but not limited to analysis of the relationship between AMG 673 dose and exposure parameters (AUC and  $C_{max}$ ) and dose proportionality assessments, may also be conducted. Based on the review of the data, analyses to describe the relationship between AMG 673 exposure and either pharmacodynamic effect and/or clinical outcome may also be performed.

**9.7.2 Analyses of Clinical Outcome Assessments**

Not Applicable

**9.7.3 Analyses of Health Economic Endpoints**

Not Applicable

**9.7.4 Analyses of Biomarker Endpoints**

Not Applicable

**10. Changes From Protocol-specified Analyses**

**Time to Progression endpoint in protocol refers to Event Free Survival, to address the Relapse/refractory AML subjects who are already in progressive state and never respond.**

**12. Prioritization of Analyses**

Not Applicable

**13. Data Not Covered by This Plan**

Not Applicable

14. Appendices

Appendix A. Imputation Rules for Partial or Missing Start Dates

The reference date for the following rules is the date of first dose [ of study drug].

Start Date		Stop Date						Missing
		Complete: yyyyymmdd		Partial: yyyyymm		Partial: yyyy		
		< 1 st dose	≥ 1 st dose	< 1 st dose yyyyymm	≥ 1 st dose yyyyymm	< 1 st dose yyyy	≥ 1 st dose yyyy	
Partial: yyyyymm	= 1 st dose yyyyymm	2	1	n/a	1	n/a	1	1
	≠ 1 st dose yyyyymm		2	2	2	2	2	2
Partial: yyyy	= 1 st dose yyyy	3	1	3	1	n/a	1	1
	≠ 1 st dose yyyy		3		3	3	3	3
Missing		4	1	4	1	4	1	1

1=Impute the date of first dose; 2=Impute the first of the month; 3=Impute January 1 of the year; 4=Impute January 1 of the stop year

Note: For subjects who were never treated (first dose date is missing), partial start dates will be set to the first day of the partial month or first day of year if month is also missing.

Imputation Rules for Partial or Missing Stop Dates

Initial imputation

- If the month and year are present, impute the last day of that month.
- If only the year is present, impute December 31 of that year.
- If the stop date is entirely missing, assume the event or medication is ongoing.

If the imputed stop date is before the start date, set stop date to missing.

If the imputed stop date is after the death date, impute as death date.

Imputation Rules for Partial or Missing Death Dates

If death year and month are available but day is missing:

[figure not shown]
- If yyyyymm for the date last known to be alive equals yyyyymm for death date, set death date to the day after the date last known to be alive.
- If yyyyymm for the date last known to be alive is less than the yyyyymm for death date, set death date to the first day of the death month.
- If yyyyymm for the date last known to be alive is greater than yyyyymm for death date, assume death date is in error, do not impute and censor the subject survival time.]

If month and day are missing and year of death is known:

- If yyyy for the date last known to be alive equals yyyy for death date, set death date to the day after last known to be alive date.
- If yyyy for the date last known to be alive is less than yyyy for death date, set death date to the first day of the death year.
- If yyyy for the date last known to be alive is greater than yyyy for death date, assume date last known to be alive is in error, set death date to the first day of the death year.

If a death date is totally missing:

Do not impute and censor the subject survival time.

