### Duration of Response (DOR)

Duration of response is defined as the interval from the date of the first disease assessment indicating an overall response to the first documented relapse or death due to any cause, whichever occurs first. Subjects without relapse or death until the analysis data cut-off date will be censored at the last adequate disease assessment date. Only subjects with a response will be evaluated for DOR.

DOR time in days = earlier of (date of first relapse or disease progression or death or date of censoring) – date of the first observation of overall response + 1.

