### Time to Progression (Event-free Survival):

Event-free survival (EFS) is defined as the interval from first administration of AMG 673 to the earliest of date of treatment failure, relapse for responders, or death due to any cause. Censoring is at the last evaluable post-baseline response assessment; otherwise, at first administration of AMG673. For non-responders, the event date for treatment failure is assigned as the date of first administration of AMG 673.

Event-free Survival in days = earlier of (date of treatment failure or relapse or death or date of censoring) – date of the first administration of AMG 673 + 1.

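### SAP Appendix A settles a death date that conflicts with the last-known-alive date in opposite directions, and its year-only rule can give impossible or falsely early durations

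*SAP*

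**What the plan says.** The rules for partial death dates are in SAP Appendix A and reappear as current wording in the replacement text of SAP Appendix C. At each level they compare the recorded death with the date last known alive.

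- **Month and year known, last-alive month later than death month:** "assume death date is in error, do not impute and censor the subject survival time".
- **Only year known, last-alive year later than death year:** "assume date last known to be alive is in error, set death date to the first day of the death year".

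The other year-only branches involve no conflict. When the two years are equal, death is set to the day after last contact. When the last-alive year is earlier, death is set to 1 January of the death year, which is after last contact.

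For adverse event and medication stop dates, the appendix has a plausibility check: "If the imputed stop date is before the start date, set stop date to missing". Death dates have no such check.

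Death is an event in two efficacy endpoints defined in SAP Section 5. EFS in days is "earlier of (date of treatment failure or relapse or death or date of censoring) – date of the first administration of AMG 673 + 1". DOR in days is "earlier of (date of first relapse or disease progression or death or date of censoring) – date of the first observation of overall response + 1". SAP Section 10 equates the protocol's time to progression with EFS.

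**The concern.** Both conflict branches face the same problem: a death recorded before a date on which the subject was reportedly alive. The SAP distrusts the death when the record is fuller and trusts it when the record is sparser, and gives no reason for the difference.

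The year-only branch also always assigns 1 January, the earliest day the record allows, without comparing that day with first dose or first response. Because EFS and DOR take the earliest qualifying date, an imputed death that comes too early displaces every real date for that subject.

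A negative duration would probably be noticed, but the SAP has no rule for it, so the repair would be devised after the data are seen. A wrong but positive duration could pass unnoticed.

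**Working it through.** The plan states no figure to reproduce. The check applies the Appendix A rules as written to assumed dates and puts the results into the Section 5 formulas.

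**Assumed inputs.** Last known alive is 10 January 2020. The death is recorded either as December 2019 or as 2019 only. First dose and first response are as in the table.

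**Step 1: the two rules.**
- Recorded as December 2019: the last-alive month is later than the death month, so no date is imputed and the subject is censored.
- Recorded as 2019: the last-alive year is later than the death year, so death is set to 1 January 2019.

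**Step 2: durations under the year-only rule.** EFS = 1 January 2019 - first dose + 1. DOR = 1 January 2019 - first response + 1. In the first row, 15 March is 73 days after 1 January, so EFS = -73 + 1 = -72. 12 April is 101 days after, so DOR = -101 + 1 = -100.

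| First dose | First response | EFS (days) | DOR (days) | Death before first dose? |
|---|---|---|---|---|
| 15 Mar 2019 | 12 Apr 2019 | -72 | -100 | yes |
| 4 Nov 2019 | 2 Dec 2019 | -306 | -334 | yes |
| 1 Jan 2019 | 29 Jan 2019 | 1 | -27 | no |
| 5 Nov 2018 | 3 Dec 2018 | 58 | 30 | no |

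The third row shows that DOR can be negative even when EFS is not, because DOR starts at response. The last row is the case that looks plausible. Its values are positive, but the death is placed 11 months before the start of the month that the fuller record would name.

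**Step 3: how often the conflict branch precedes treatment.** If first dose falls in the recorded death year (365 days), the imputed death is before first dose for 364 of the 365 possible dates, all but 1 January. EFS then runs from +1 (first dose 1 January) through 0 (2 January) to -363 (31 December). If first dose was in an earlier year, the imputed death is not before treatment.

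**Step 4: the other year-only branches.** In the equal-year branch, none of 152 first-dose dates checked gave a death before first dose. The earlier-year branch cannot do so if last contact is on or after first dose. The fault is confined to the conflict branch.

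**Step 5: who is affected.**
- *Responder without documented relapse:* the month rule leaves DOR and EFS censored; the year-only rule makes each an event.
- *Responder with relapse:* an event exists already, but an earlier imputed death would replace its date.
- *Non-responder:* SAP Section 5 already places the EFS event at first dose (EFS = 1 day). An imputed death after first dose changes nothing; one before it moves the event to an impossible value. DOR does not apply.

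**The case against.** The case for leaving this alone has weight.

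- **The trigger is rare.** It needs a year-only death date and a last-alive date in a later calendar year. Protocol Appendix B asks for the date of death on fatal event reports, Section 9.2.2.2 requires serious events within 24 hours, and the end-of-study visit comes about 4 weeks after last dose. Section 12.3 already has data management check for discrepancies and query sites. This stands. However, Section 12.4 lets investigators search public records for survival status, a possible source of incomplete dates.
- **Which field to trust is a convention.** This also stands. Believing the death record is not wrong in itself; the defect is that the direction changes with the completeness of the record.
- **Little depends on it.** SAP Section 9.5.2 calls the efficacy analyses exploratory, and the Kaplan-Meier curve is optional. No overall survival endpoint is visible, although the exploratory endpoints cannot be seen.

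Stronger readings are tempting but not supported.

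- A reader might infer that the rule replaces all the time to last contact with a false early event. In the first example, that interval is 291 + 10 = 301 days, about 10 months. But Section 5 censors DOR at the last adequate disease assessment and EFS at the last evaluable post-baseline response assessment, not at last contact. The true contrast depends on assessment dates and is no larger than that interval implies.
- A reader might infer that every affected subject changes from censored to event. For EFS that is untrue of non-responders.
- A reader might infer an effect on safety conclusions or dose selection. The imputed death can cap imputed stop dates ("If the imputed stop date is after the death date, impute as death date"), but stop dates do not determine adverse event incidence or grade, and DLTs come from a flag on the Events eCRF.

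**Conclusion.** The point holds as a minor one. Appendix A resolves one contradiction in two opposite ways. Followed literally, its year-only branch produces a death before treatment whenever first dose falls after 1 January of the recorded death year. The resulting EFS is zero or negative, down to -363 days when first dose is in that year, and DOR is negative for any response after first dose. With first dose in an earlier year, the rule can give a falsely early event that looks valid.

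This rests on two assumptions: that the Appendix A death rules feed the death component of EFS and DOR (the month rule speaks only of survival time), and that a year-only conflict survives the query process. First dose and recorded death in the same calendar year is plausible, since Protocol Section 3.5.1 expects participation of up to 12 months. The example dates are illustrative, and the documents give no basis for a frequency. Rarity and exploratory status limit the consequence but do not make the rule correct. The effect would be most visible in DOR, which uses responders only, in an expansion cohort of up to 10 subjects.

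**What to change.** Replace the year-only conflict branch in SAP Appendix A with the month-level rule. If the last-alive year is later than the recorded death year and the routine site query does not resolve it, do not impute a death date. For subjects with no other event, censor DOR at the last adequate disease assessment and EFS at the last evaluable post-baseline response assessment, as SAP Section 5 already defines. Non-responders keep their EFS event at first dose.

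A programmed check that no imputed death precedes first dose is an optional safeguard. Once the conflict branch is changed, the remaining branches cannot produce such a date if last contact is on or after first dose.

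The cost is one SAP line and the matching line of code, with no effect on data collection, sample size or the primary analysis. It should be settled before database lock.
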